5.4 Prohibited Concomitant Medication

The Biohaven Medical Monitor should be contacted to discuss any subjects who have been previously treated with riluzole. Treatment with riluzole in the 60 days prior to randomization and during the study is prohibited. Subjects with prior use of riluzole who discontinued due to tolerability or lack of clinical benefit (in the opinion of the Investigator) are not eligible for this Approved Version 08; 17 April 2020

study. Reasons for discontinuation of riluzole should be documented in the subjects' medical chart.

Woman of Childbearing Potential

Women of childbearing potential (WOCBP) include any female who has experienced menarche and who has not undergone successful surgical sterilization (hysterectomy, bilateral tubal ligation, or bilateral oophorectomy) or is not postmenopausal. Post menopause is defined as:

- Amenorrhea greater than or equal to 12 consecutive months without another cause and a documented serum follicle stimulating hormone (FSH) level > 35mIU/mL or;
- Woman with irregular menstrual periods and a documented serum follicle stimulating hormone (FSH) level > 35mIU/mL or;
- o NOTE: FSH level testing is not required for women greater than or equal to 62 years old with amenorrhea of greater than or equal to one year;
- Woman on hormone replacement therapy (HRT).

The requisite drug interaction studies to determine the interaction of troriluzole with oral contraceptives have not been performed to date. It is therefore not possible to determine the efficacy of oral contraceptives as an effective method of contraception for WOCBP who participating this study. Oral estrogen and progestin hormonal contraceptives as a sole method of contraception are therefore prohibited. It is required that all WOCBP use two methods of contraception for the duration of the study (i.e. beginning at 30 days prior to baseline) through 30 days after the last dose of study drug. The two methods should include one barrier method (e.g. diaphragm with spermicidal gel, condom with spermicidal gel, intrauterine devices, cervical cap) and one other method. The other method could include oral contraceptives or another barrier method.

Any male who has a female partner of WOCBP has to avoid becoming pregnant while participating in this study. If male subjects are sexually active and not vasectomized for at least 6 months, and if the subject's female partner is not surgically sterile or is not post-menopausal, then one of the following accepted methods of contraception should be used throughout the study and for 90 days after the last study drug administration:

Simultaneous use of male condom, and for the female partner, hormonal contraceptives (e.g., birth control pills, implants, patch, depot injection, used since at least 4 weeks) or intra-uterine contraceptive device (placed since at least 4 weeks) before sexual intercourse;

• Simultaneous use of male condom, and for the female partner, diaphragm with intravaginally applied spermicide.

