5.2 Inclusion Criteria

1. **Informed Consent**

[figure not shown]
a. Subjects (or legally acceptable representative as required by the IRB/IEC) must provide a written signed informed consent form/forms (IRB/EC specific) prior to the initiation of any protocol required procedures.

2. Age and Sex

a. Male and female outpatient subjects between the ages of 18 - 75, inclusive

3. Target Population

a. Subjects with a known or suspected diagnosis of the following specific hereditary ataxias: SCA1, SCA2, SCA3, SCA6, SCA7, SCA8 and SCA10;

- b. Ability to ambulate 8 meters without assistance (canes and other devices allowed);
- c. Screening total SARA total score ≥8;
- d. Score of ≥ 2 on gait subsection of the SARA;
- e. Determined by the investigator to be medically stable at Baseline/randomization as assessed by medical history, physical examination, laboratory test results, and electrocardiogram testing. Subjects must be physically able and expected to complete the trial as designed;

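### Two of the three routes to post-menopausal status in protocol section 5.4 have no amenorrhea condition, so possibly fertile women fall outside the contraception rule and scheduled pregnancy tests

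*Protocol*

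**What the plan says.** Protocol section 5.4 defines a WOCBP as a female past menarche who has not been surgically sterilized, and continues "or is not postmenopausal. Post menopause is defined as", followed by three alternatives joined by *or*:

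1. "Amenorrhea greater than or equal to 12 consecutive months without another cause and a documented serum follicle stimulating hormone (FSH) level > 35mIU/mL".
2. "Woman with irregular menstrual periods and a documented serum follicle stimulating hormone (FSH) level > 35mIU/mL or". A note beneath this route waives the FSH test for "women greater than or equal to 62 years old with amenorrhea of greater than or equal to one year".
3. The whole of the third is "Woman on hormone replacement therapy (HRT").

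The section then states: "It is required that all WOCBP use two methods of contraception for the duration of the study". Section 6.2.4.4 and the test rows of Tables 2 to 5 direct scheduled pregnancy tests to WOCBP. For male subjects, section 5.4 applies a contraception rule when the "female partner is not surgically sterile or is not post-menopausal". Eligibility by age is broad: "Male and female outpatient subjects between the ages of 18 - 75, inclusive" (section 5.2). Section 1.1.7 says that fertility and fetal development studies have not yet been done.

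**The concern.** The protocol sets a standard for menopause and then bypasses it twice. Route 1 needs a year without periods and a raised FSH. Route 2 accepts the same FSH from a woman who, by its own description, still has periods; one documented value is enough, with no limit on its date or on her age. Route 3 asks for no amenorrhea, FSH or age. Even the note for women aged 62 or over keeps the one-year amenorrhea condition and waives only the blood test.

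Post-menopausal status decides whether a woman must use contraception and whether she is tested on schedule. With no fetal data, open-label treatment of up to 192 weeks and a possible increase to 280 mg, these two safeguards are what the protocol relies on to prevent or detect an exposed pregnancy early. Routes 2 and 3 remove both for women whose fertility has not been shown to have ended.

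**Working it through.** The plan gives no figure on this point, so the check is a comparison of texts followed by a count of visits.

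**Step 1. Which reading of the WOCBP sentence applies.** Let S mean surgically sterilized and P mean post-menopausal by one of the three routes. As written, the sentence gives WOCBP = (not S) or (not P). The evident intention is WOCBP = (not S) and (not P).

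| Woman | S | P | WOCBP as written | WOCBP as intended |
|---|---|---|---|---|
| Irregular periods, FSH >35 | no | yes | yes | no |
| On HRT | no | yes | yes | no |
| 12 months' amenorrhea, FSH >35 | no | yes | yes | no |
| Regular cycles | no | no | yes | yes |
| Sterilized, not post-menopausal | yes | no | yes | no |

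As written, only a woman both sterilized and post-menopausal would be outside the group, and neither exemption would work alone. The intended reading is the only one that gives the definition of menopause any effect.

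**Step 2. What each route requires on the intended reading.**

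| Route | Amenorrhea | FSH >35 mIU/mL | Age limit |
|---|---|---|---|
| 1 | at least 12 months, no other cause | yes | none |
| Note | at least 1 year | waived | 62 or over |
| 2 (irregular periods) | none | one documented value | none |
| 3 (HRT) | none | none | none |

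**Step 3. Scheduled post-dose visits with a WOCBP pregnancy test.**

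- Table 2: Weeks 4 and 8 = 2.
- Table 3: Weeks 4, 8, 12, 24, 36 and 48 = 6 (the conditional baseline visit is not counted).
- Table 4, continuing subjects: Weeks 60 to 192 every 12 weeks = (192 − 60)/12 + 1 = 12.
- Table 5, returning subjects: Weeks 12 to 144 every 12 weeks = (144 − 12)/12 + 1 = 12.
- First dose to the end, either path: 2 + 6 + 12 = 20.

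Tests that subjects take between office visits, described in the table footnotes, are not counted.

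**Step 4. How many lay ahead at version 08 (17 April 2020).**

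- Lower figure: the 48 weeks added by version 08 hold Weeks 156, 168, 180 and 192 (continuing) or 108, 120, 132 and 144 (returning) = 4.
- Upper figure: section 9 of the SAP addendum (27 March 2020) mentions data locked through Extension Week 48. If that means every subject had passed that visit, at most the 12 visits of Table 4 or Table 5 remained.

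**The case against.** **The literal wording protects these women.** Taken word for word, every unsterilized woman stays WOCBP. That is true, but it also makes WOCBP of sterilized premenopausal women and of women who meet route 1. A site would not apply it so. The ambiguity is a reason to correct the sentence, and a fix that changed only the routes would be incomplete.

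**Text has been removed.** The lettering of section 5.3 has gaps, and sections 6.2.4.1 to 6.2.4.3 are not visible, so another reproductive criterion or an FSH test could sit there. This stands as a limit: the finding is that no *visible* text restores an amenorrhea condition. FSH is not in the visible laboratory panel either, which makes route 2 narrower in practice, since a result would have to come from elsewhere.

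**Section 6.2.4(d) prescribes urine pregnancy tests without naming WOCBP.** It could be read as covering all women. Section 6.2.4.4 and the schedule rows, which are the specific provisions, limit the tests to WOCBP, and the contraception rule does so too.

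**Protection remains.** The investigator may test at discretion (section 6.2.4.4) or on suspicion (Table 2), women are told to report a pregnancy (section 8.1.5), and a positive test ends participation. A reader might infer that these women have no safeguard at all; the documents do not support that. What is lost is contraception and the tests that need no one to suspect a pregnancy.

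**Nobody may be affected.** Since entry starts at 18, a reader might infer that young women on HRT were enrolled and exempted. The rule would permit it, but nothing shows that it happened.

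**Conclusion.** The point holds as a fault in a safety rule. On the evidently intended reading, a woman with irregular periods and one FSH above 35 mIU/mL, or any woman on HRT, is classed as post-menopausal without an amenorrhea condition. She is then outside the two-method rule and the scheduled tests.

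Its size is limited. For each completing woman so classed, about 4 to 12 scheduled test visits were still ahead at version 08. The 12 depends on the assumption about the Week 48 data lock, which the addendum mentions only for Randomization Phase ad hoc analyses; without it the count could be higher, with 20 from first dose as the ceiling. It would be tempting to report 20 as the loss, but that covers the whole trial, much of it already past. These are schedule counts, not a measure of harm, and the number of women they apply to is unknown and possibly zero. The documents show no exposed pregnancy arising from this rule. The primary SARA analysis is untouched.

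The change should still be made, because the fault is specific and the correction adds no new type of test.

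**What to change.** Amend protocol section 5.4:

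1. In the WOCBP sentence, join the two conditions with *and*, so that a woman is WOCBP if she is neither sterilized nor post-menopausal. Make the same correction in the sentence on partners of male subjects.
2. Delete the irregular-periods route.
3. Limit the HRT route to women whose records show that, before HRT began, they met the protocol's own standard: at least 12 months of amenorrhea without another cause plus FSH >35 mIU/mL, with FSH waived at age 62 or over with at least one year of amenorrhea. Treat other women on HRT as WOCBP.
4. At the next scheduled visit, re-check women classed as post-menopausal only by route 2 or 3. For any who become WOCBP, start contraception and the tests already in the schedule from that visit. The existing start of 30 days before baseline cannot be met by women already on treatment, so this transition rule must be written in.

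The cost is an amendment with IRB/IEC approval before use and possibly renewed consent (section 11), plus one check of records at a visit already planned. Some women who are in fact post-menopausal, including older HRT users without records, would have to use two methods and be tested. The tests themselves are already in the schedule.

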5.5 Deviation from Inclusion/Exclusion Criteria

Any significant event that does not comply with the inclusion exclusion criteria, study conduct, or study procedures will be documented as a deviation. Deviations will be documented and reported through the clinical monitoring of the trial. Deviations will be reported to the IRB/EC at the frequency required by your IRB/EC. There will be no protocol exceptions granted by the Sponsor for Inclusion/Exclusion criteria.

6 STUDY CONDUCT AND DESCRIPTION OF STUDY PROCEDURES

6.1 Study Materials

The sponsor will provide investigational product which will include including troriluzole, 140 MG capsules and matching placebo.

Sites will also be provided with a Regulatory binder, Rating Scale Binder, IVRS Manual and a Source Document Template. Instructions on all specimens collected will be provided by a central laboratory.

All sites will use an Electronic Data Capture (EDC) tool to submit study data. Electronic Case Report Forms (eCRFs) will be prepared for all data collections.

Sites will be provided with a Biohaven approved protocol and any amendments.

The investigator will be required to have a centrifuge, a secure locked cabinet or similar (for drug storage) as well as appropriate containers and dry ice for shipment and storage of blood and plasma samples. Enough dry ice, when indicated, should be utilized to allow samples to arrive at their designated laboratory in a frozen state.

Eligibility Assessments

6.1.1 Mini Mental State Examination (MMSE)

The MMSE is a 30-point (11-question) measure commonly used to measure cognitive impairment. It tests five areas of cognitive function including orientation, registration, attention and calculation, recall and language.

6.1.2 Neurological Exam

A neurological examination will be performed by a trained examining neurologist, which will involve mental status/cognition, cranial nerves, motor system, sensory system, reflexes and coordination/gait. The examination should be carefully documented in the subject's medical and/or study chart.

6.1.3 Medical History

A full medical history will need to be obtained at the screening visit. This will include but is not limited to: smoking history, cardiovascular disease, and family history of ataxia, if available.

6.2 Safety Assessments

Safety and tolerability will be evaluated by report of adverse events (AE) and by evaluation of abnormalities and clinically significant changes in physical examinations, ECGs, vital signs, and laboratory tests.

The SARA rating (primary outcome measure) must NOT be performed by the staff (including principal investigator) who are evaluating test lab results during the 8 week randomization phase. Specifically, these tests include Serum Chemistry, Hematology and Urinalysis acquired after baseline (i.e., Week 4 scheduled labs, potentially other unscheduled tests, through Week 8 scheduled labs). After completion of the Week 8 visit assessments and sign-off on SARA ratings as final, a SARA rater who is the principal investigator may evaluate labs that will be acquired within the Extension Phase. Based on this requirement, a site may potentially need to identify a qualified physician or other medical personnel who can be available to review lab tests during the randomization phase for each subject. This is further described in Section 6.3.1.

6.2.1 Vital Signs and Physical Measurements (Height and Weight)

Sitting vital sign measurements (temperature, blood pressure, and heart rate) will be recorded during the scheduled visits as specified in the Schedule of Assessments/Time & Events and as medically necessary.

Body weight and height will be recorded at scheduled visits. The following guidelines will aid in the standardization of these measurements.

- 1) The same scale should be used to weigh a given subject throughout the study.
- 2) Scales should be calibrated and zeroed just prior to each subject's weigh-in session.
- 3) A subject should void just prior to being weighed.
- 4) Weight should be recorded before a meal (if applicable) and at approximately the same time each day.
- 5) A subject should be minimally clothed (i.e., no shoes or heavy garments).

6.2.2 Electrocardiogram (ECG)

A 12-Lead ECG will be recorded during the scheduled visits as specified in the Schedule of Assessments/Time & Events and as medically necessary. Any abnormal ECGs should be reviewed by a cardiologist to determine clinical significance. If a site is unable to identify a cardiologist for this task, the Medical Lead at ECG to determine clinical significance.

6.2.3 Physical Exam

[figure not shown]
Subjects will undergo a complete physical exam in both the Randomization and Extension Phase of the study. The Physical Exam should include at least the following components: HEENT (head, eyes, ears, nose, and throat), neck, chest (breast) and lungs, cardiovascular, abdomen, skin, and musculoskeletal evaluation by the Principal Investigator or a medically qualified delegate.

6.2.4 Laboratory Assessments

Laboratory testing will include the following:

- a) Hematology: hemoglobin, hematocrit, platelets, CBC with differential and absolute neutrophil count
- b) Serum Chemistry: sodium, potassium, chloride, calcium, ALT, AST, LDH, alkaline phosphatase, GGT, phosphorous, bicarbonate, CPK, total protein, albumin, total bilirubin (if greater than 2 mg/dl bilirubin will be fractionated), glucose, creatinine, BUN, uric acid, and pregnancy testing (WOCBP). Additionally, at screening, total cholesterol, LDL, HDL, triglycerides, folate, HbA1C, P-Amylase or Lipase, TSH, and T4:
- c) Urinalysis: macroscopic examination, pH, specific gravity, ketones, nitrites, urobilinogen, leukocyte esterase, protein, creatinine, glucose, and occult blood will be performed during the scheduled visits as specified in the Schedule of Assessments/Time & Events and as medically necessary. If blood, protein, or leukocytes, are positive microscopic examination will be performed on abnormal findings;
- d) Urine pregnancy tests will be performed 72 hours prior to dosing at Baseline, at study visits where lab assessments are not performed, or at the discretion of the Investigator;
- e) HBsAg, HCV and HIV antibody detection will be performed at screening.

Any lab value outside of the normal range must be brought to the attention of a physician (Investigator or Sub-Investigator) at the site. The Investigator will indicate whether or not a flagged value is of clinical significance. In addition, if warranted repeat labs can be drawn. Any local lab results that are out of range must be brought to the attention of the Biohaven Medical Monitor.

6.2.4.4 Pregnancy Testing

Pregnancy testing should be performed on all women of childbearing potential (WOCBP) during both the Randomization Phase and Extension Phase of the study. Refer to the Schedule of Assessments/Time & Events for detailed time points in which serum pregnancy tests and urine pregnancy tests are required. Urine pregnancy testing may also be done at the discretion of the Investigator at any time during the study. Subjects should not continue in the study if the pregnancy test is positive at any time.

6.2.4.5 Evaluation of Laboratory Assessments

As described above, the SARA rating (primary outcome measure) must NOT be performed by the staff (including principal investigator) who are evaluating test lab results during the 8 week randomization phase. Specifically, these tests include Serum Chemistry, Hematology and Urinalysis acquired after baseline (i.e., Week 4, potentially other unscheduled tests, through Week 8 scheduled labs). After completion of the Week 8 visit assessments and sign-off on SARA ratings as final, a SARA rater who is the principal investigator may evaluate lab tests acquired in the Extension Phase. Based on this requirement, a site may potentially need to identify a qualified Lab Monitor (i.e., physician or other medical personnel) who can be available to review labs during the randomization phase for each subject. This requirement does not apply during the Extension Phase.

The rationale for this process is to assure adequate blinding while maintaining subject safety. Riluzole itself is associated with low rates of transient increases in transaminases. According to the US Prescribing information for riluzole (the active metabolite of troriluzole), the rates of markedly elevated transaminases (AST or ALT > 5x ULN) are approximately 2%. The rates of less elevated transaminases (i.e., AST or ALT > 3x ULN) are approximately 8%. While troriluzole was designed to diminish risk for LFT changes (e.g., diminished first-pass liver metabolism, approximately 30% lower molar burden than the 100 mg dose of riluzole), the study is designed to address the possibility of such increases while maintaining the integrity of the primary outcome measure. Other lab abnormalities, based on known literature of riluzole, could include decreased neutrophil count. The Lab Monitor should manage any non-LFT lab Approved Version 08: 17 April 2020

abnormalities as medically warranted to assure subject safety. The SARA Rater (who may be the PI) should be shielded from the nature of any additional evaluation triggered by these lab tests.

The management of abnormal LFTs are described herein. Scheduled LFTs (ALT, AST, bilirubin, alkaline phosphatase) at the Week 4 and Week 8 visits will be evaluated by the Lab Monitor (LM), who will be a physician or other qualified medical personnel designated by the PI and who has no involvement in the conduct of the SARA Ratings.

If AST or ALT values are between 3x ULN and <5x ULN, then the Lab Monitor, potentially with administrative assistance from the Study Coordinator, will medically evaluate the subject. Medical assessment of the subject can include the following:

- Must include repeat LFT assessments (ALT, AST, total and direct bilirubin, alkaline phosphatase, PT, aPTT, INR) within 1 week and follow until resolution. The frequency of the repeat tests will be clinically based on trajectory of change (e.g., improving, stable vs increasing). These tests can be performed either at a local, or preferably, central lab
- Assessment of AEs, usage of concomitant medications, exposure to potential hepatic toxins, risk factors for hepatitis or alcoholic liver disease
- Based on overall clinical presentation (severity and extent of lab abnormalities; rate of change of lab values), additional evaluations (as outlined under the scenario of ALT/AST > 5xULN) may be considered.

If the Week 4 visit shows ALT or AST>5x ULN, the Lab Monitor will notify the PI and the PI will assess this as a potential SAE. The subject will be managed as appropriate, including:

- Study medication must be discontinued immediately
- Bring subject in for physical exam and evaluation.
 - Assess for right heart failure, hypotension, and signs/symptoms of alcohol abuse
 - o assess for exposure to toxic dietary/herbal supplements and/or prescriptions drugs that are associated with hepatic effects, such as acetaminophen;
 - o assess for potential exposure to environmental toxins
 - o Evaluate for abdominal pain, splenomegaly, hepatomegaly
- Repeat LFTs (AST, ALT, total and direct bilirubin, alkaline phosphatase) as soon as possible, with either a local lab or preferably central lab; and, follow to resolution;
- Order other labs tests to rule-out other causes of lab abnormalities and to assess extent of hepatic effects
 - o coagulation factors (PT, aPTT, INR)
 - o Hepatitis A, B and C serologies
 - o Ebstein-Barr virus serology
- Assess AEs
- Consider gall bladder or ductal imaging studies if presentation suggests potential for gall stones.

Entry into the Extension Phase requires continued impression that open-label treatment offers an acceptable risk-benefit profile. If lab abnormalities in the Randomization Phase are potentially clinically significant then treatment with study drug in the Extension Phase should

not begin until such labs near normal limits or in the case of elevated transaminases (ALT or AST) are within 3x ULN. If results from the scheduled Week 8 assessment show emergence of potentially clinically significant lab abnormalities and the subject has already started open-label troriluzole, then labs must be repeated and the LM, based on clinical impression concerning the nature and severity of results, may decide to continue troriluzole. In the case of AST or ALT > 5 x ULN, re-challenge with study drug will not be allowed.

Other Safety Assessments

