7.2.1 Method of Assigning Patient Identification

The investigator or designee will need to access an Interactive Web-based Response System (IWRS) in order to register each subject in each study phase. Initially the investigator or designee will enter the subject into the study at the Screening Visit after informed consent is obtained and a subject number will be assigned. After completion of all screening evaluations, all eligible subjects will be randomized, in a 1:1 ratio

to receive either placebo (QD) or troriluzole (140mg QD). Treatment assignments will be obtained by the investigator (or designee) via the IWRS system.

Investigational sites will access the IWRS at each scheduled study visit throughout the Randomization Phase. The IWRS system will assign specific bottle numbers for all blinded study drug to be dispensed to the subject. Once a bottle has been assigned it cannot be dispensed to another study subject.

Once a subject completes the Randomization Phase or if a subject is discontinued early from the study, the investigator or designee must access the IWRS to discontinue the patient from participation in the study.

Subjects who complete 8 weeks of treatment in the Randomization Phase may be eligible for an Extension Phase of the study. The investigator or designee must access the IWRS to enter the subject in the Extension Phase. Investigational sites will access the IWRS at each scheduled study visit throughout the Extension Phase to track patient enrollment.

Open Label Extension study medication will be supplied in bulk bottles. Bottle numbers will be assigned via the IWRS system in the Extension Phase. Sites will be responsible for recording the bottle numbers dispensed to the subject on the Drug Accountability Form provided in the Regulatory Binder, as well as ensure appropriate documentation of dispensation in the subject's medical record. Once a subject completes the Extension Phase or if a subject is discontinued early from the Extension Phase of the study, the investigator or designee must access the IWRS to document the discontinuation of the subject from participation in the study.

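### Protocol 6.2.4.5 ties its mandatory stop for ALT/AST above 5x ULN to the Week 4 visit, so a Week 8 result at that level can be read as allowing open-label troriluzole to continue

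*Protocol*

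**What the plan says.** Protocol 6.2.4.5 presents itself as the liver-test guidance ("The management of abnormal LFTs are described herein") and assigns the scheduled Week 4 and Week 8 liver tests to a Lab Monitor who takes no part in the SARA ratings.

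It has two tiers. The tier from 3x to below 5x ULN names no visit and calls for repeat tests and medical evaluation. The tier above 5x ULN begins "If the Week 4 visit shows ALT or AST>5x ULN, the Lab Monitor will notify the PI". Its first action is "Study medication must be discontinued immediately", followed by examination, repeat tests, a search for other causes and assessment as a possible SAE.

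Week 8 results are handled separately. A subject who has not yet started open-label drug may not start until transaminases are within 3x ULN. If open-label troriluzole has already begun, "then labs must be repeated and the LM, based on clinical impression concerning the nature and severity of results, may decide to continue troriluzole". The section then ends its liver text with "In the case of AST or ALT > 5 x ULN, re-challenge with study drug will not be allowed".

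Other visible rules bear on the same result. Section 6.2.4 states "Any lab value outside of the normal range must be brought to the attention of a physician (Investigator or Sub-Investigator) at the site" and sends out-of-range local results to the sponsor's medical monitor. Section 4.1 permits a step down from 280 mg to 140 mg for clinically significant laboratory abnormalities. Section 8.1.6 defines potential drug-induced liver injury.

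**The concern.** The same value leads to different instructions at two visits four weeks apart. At Week 4, an ALT above 5x ULN stops the drug with no discretion. At Week 8, with open-label drug already started, the text gives discretion without a ceiling and then forbids re-challenge. That word normally means restarting after a stop, and nothing in the Week 8 text orders a stop. The two tiers are also worded differently, one without a visit and one with, so a site could take the Week 4 limit as deliberate.

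What is at stake is subject safety and consistency between sites. Protocol 10.1 provides no data monitoring committee and relies on close monitoring through the sites, so the site-level rule is a main safeguard. SAP 4.8.2 and 4.8.3 tabulate discontinuations due to AEs and the category above 5x ULN for the Extension Phase. Two sites could therefore record different outcomes for the same laboratory result.

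**Working it through.** **Step 1. The instructions side by side, for ALT or AST above 5x ULN**

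| Situation | What the visible text orders |
|---|---|
| Week 4, double-blind | PI notified, immediate stop, full work-up (6.2.4.5) |
| Week 8, open-label drug not started | No start until within 3x ULN (6.2.4.5) |
| Week 8, open-label drug started | Repeat labs; Lab Monitor may continue; no re-challenge (6.2.4.5) |
| Unscheduled test, randomized phase | Not named in the tier above 5x ULN |
| Extension, 140 mg | No stop in the visible text; physician review (6.2.4) |
| Extension, 280 mg | As above; dose may be reduced to 140 mg (4.1) |

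**Step 2. Does another visible rule force a stop?** Take an isolated ALT of 6x ULN with normal bilirubin, in a subject on open-label drug.

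- Section 8.1.6 also requires bilirubin above 2x ULN and no other apparent cause. It is not met. If it were met, the action would be to contact the medical monitor, with no automatic stop.
- Section 6.2.4 requires a physician to see the value but prescribes no action on the drug.
- Section 4.1 is permissive and gives no transaminase level.

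None of these forces a stop.

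**Step 3. The two readings of the Week 8 text.** (A) The Lab Monitor may continue at any level, and only a restart after stopping is barred. (B) Above 5x ULN the drug must stop and stay stopped. The words fit both.

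**Step 4. Size.** The plan gives no figure for this point. Its power calculation (56 per group, about 90%) reproduces at 0.899 by the exact t calculation and plays no part here.

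Inputs:
- about 120 randomized (Protocol 5.1)
- 1:1 allocation (Protocol 7.2.1: "all eligible subjects will be randomized, in a 1:1 ratio"), so about 120/2 = 60 per arm
- a riluzole rate above 5x ULN of about 2% (6.2.4.5)

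Assumptions: the 2% carries over to troriluzole (1% shown as a lower case), and 70% to 100% of subjects enter the extension, since uptake is not given.

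Formulas: expected number = N × p; chance of at least one = 1 − (1 − p)^N.

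| Group | N | p | Expected | Chance of at least one |
|---|---|---|---|---|
| On troriluzole in the randomized phase | 60 | 2% | 1.2 | 1 − 0.98^60 = 0.702 |
| Placebo subjects first exposed in the extension | 42 to 60 | 2% | 0.84 to 1.2 | 0.572 to 0.702 |
| All extension entrants | 84 to 120 | 2% | 1.68 to 2.4 | 0.817 to 0.911 |
| All extension entrants | 84 to 120 | 1% | 0.84 to 1.2 | 0.570 to 0.701 |

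The first row spans all draws of those 60 subjects, so the number at Week 8 alone is smaller. If a site's choice to continue or stop changed one subject's status, the extension discontinuation percentage would move by 1/120 = 0.83 to 1/84 = 1.19 percentage points. How often a site would in fact continue is not known.

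**The case against.** Five points can be made against this.

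- **Purpose.** Section 6.2.4.5 mainly protects the blind of the SARA rater. Week 4 is the only scheduled on-treatment draw with double-blind dosing still ahead, which explains why the stop names it. This stands as an explanation, but the section also takes on Week 8 results explicitly and leaves that rule open.
- **Intent.** The re-challenge sentence directly follows the discretion sentence and singles out values above 5x ULN. Reading A would allow uninterrupted dosing while forbidding a restart, which is odd. Reading B is probably intended, and a reader who inferred a flat contradiction would go too far. The text still does not order the stop.
- **Visibility.** Sections 6.2.4.1 to 6.2.4.3 and the start of 6.5 cannot be seen in the public version. A reader might infer that the protocol has no transaminase stopping rule after Week 4. The documents do not support that, because such a rule could stand in those sections. This objection stands in full for the Extension Phase and 280 mg.
- **Safeguards.** A reader might infer that extension subjects are unprotected. They are not. Every out-of-range value goes to a physician. Liver tests are local from expanded-extension Week 108 (continuing subjects) or Week 60 (returning subjects), so out-of-range results then go to the medical monitor. For continuing subjects that covers 8 of 18 scheduled on-drug extension draws. SAP addendum Section 8 also requires a narrative for each troriluzole-treated subject with on-treatment ALT or AST above 3x ULN. These measures reduce divergence between sites but prescribe no drug action.
- **Size.** Troriluzole was designed to lower liver risk, so 2% is likely high. It is also tempting to say that the stop names only 1 of 20 scheduled on-drug draws for a troriluzole-randomized subject (Week 4, Week 8 and 18 in the extension). That overstates the gap, because the section does not set out to manage most of those draws.

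**Conclusion.** The point holds as a minor one and a cheap improvement. In 6.2.4.5 the mandatory stop and work-up depend on the Week 4 visit. The Week 8 text can be followed by continuing open-label drug at a level that forces a stop at Week 4. This part rests on visible text alone.

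The further statement, that the stop should also cover the Extension Phase at 140 mg and 280 mg, assumes that the non-visible sections contain no study-wide stop.

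The number of subjects concerned is about 1 to 2 if the riluzole rate carries over, and probably fewer. The documents give no rate for 280 mg. The 8-week randomized comparison, its alpha, its power and its sample size are unaffected, and the extension safety tables are descriptive.

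**What to change.** First confirm that 6.2.4.1 to 6.2.4.3 and 6.5 do not already contain a study-wide stop. Then make two changes in 6.2.4.5:

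1. Replace the Week 4 condition with: *If any on-treatment result (Week 4, Week 8, unscheduled, or Extension Phase at 140 mg or 280 mg) shows ALT or AST >5x ULN*. State that the PI acts where no Lab Monitor is in place. Keep the existing stop, work-up and no-re-challenge text.
2. Limit the Week 8 sentence that lets the Lab Monitor continue troriluzole to ALT and AST at or below 5x ULN.

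The cost is one or two sentences and a letter to sites, with no new visits, tests or data. The downside is that investigators lose discretion for very few subjects (about 1 to 2 on the 2% assumption). Protocol 4.4 offers those subjects no other access to study drug after the extension.
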